5.2. Study Flow Chart for patients entered from Study SGT-54-01 or SGT-54-02

Procedure	Visit 2 ^{1,2,7}	Visit 3, 4, 6, 7, 9, 10	Visit 5, 8, 11	Visit 12 (EOT ³ /EOS ⁴)	Unscheduled Visit ¹¹
Name of Visit	Baseline Day 1	Week 4, 8, 16, 20, 28, 32 ⁵ Day 29, 57, 113, 141, 197, 225	Week 12, 24, 36 ⁵ Day 85, 169, 253	Week 40 Day 281 ⁶	
Visit window		± 10 days	± 10 days	± 10 days	
Entry Criteria	X				
Sign Informed Consent	X				
Demographics	X				
Medical History/Previous Therapies	X				
Con med	X	X	X	X	X
Pregnancy Test ⁷	X	X	X	X	X
Brief Physical Examination	X		X	X	X
Cutaneous Safety Assessment and Local Tolerability Assessments	X	X	X	X	X
Administer/ Review Patient Instructions	X	X	X		X
IGA ⁸	X	X	X	X	X
Rosacea Erythema Assessment	X	X	X	X	X
Telangiectasia Assessment	X	X	X	X	X
Weigh Study Product	X	X	X	X	X
Study Product Dispensed ⁹	X	X	X		X
Provide Cleanser and Moisturizer/Sunscreen, if needed	X	X	X		X
Study Product Collected		X	X	X	
Diary Card dispensed	X	X	X		X
Diary Card collected		X	X	X	X
Adverse Events	X	X	X	X	X
Complete RosaQoL ¹⁰	X		X	X	

¹ Patient will be eligible for the extension study only after completing 12 weeks of one of the two Phase 3 studies SGT-54-01 or SGT-54-02 at the Week 12 window time (± 4 days) and missed not more than one visit of Visits 3, 4 or 5 in these studies.

² Same Visit as Visit 6 in Phase 3 Study SGT-54-01 or Study SGT-54-02. All procedures that were performed in Visit 6 of Study SGT-54-01 or Study SGT-54-02 will be captured in the Study SGT-54-07 source document.

³ EOT – end of treatment.

⁴ EOS – end of study.

⁵ All visits must be in reference to baseline and counted accordingly.

⁶ All Week 40 procedures should be completed for Patients who terminate early.

⁷ Urine test for women of childbearing potential.

⁸ For product dispensing eligibility

⁹ The dispensation and usage of the pump is based on IGA score.

¹⁰ RosaQoL is a Rosacea Quality of Life questionnaire

¹¹ Perform procedures per PI discretion.

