13.16. Unscheduled Visit

An unscheduled visit is allowed at any time if in the investigator's opinion it is warranted. The following procedures may be performed at the unscheduled visit, if required.

- Observe and query the patient in a non-directive fashion about any adverse events since the previous study visit
- Query the patient about any changes in concomitant therapies since the previous study visit and update the Concomitant Therapy eCRF
- Perform brief physical examination and vital signs as described in [Section 13.7](#)
- Perform a urine pregnancy test
- Perform the IGA described in [Section 14.1](#), rosacea erythema assessment and telangiectasia assessment described in [Sections 14.2 to 14.4](#)
- Perform Cutaneous Safety Assessment and Local Tolerability Assessment as described in [Sections 15.1 to 15.2](#)
- Review the patient's compliance with the study requirements; collect and review the Patient Diary Card
- Dispense a Diary Card to the patient

- Dispense cleanser and moisturizer with sunscreen if needed
- Review the study product application instructions with the patient
- Weigh and dispense the next pump of study product
- Remind patient to not wear make-up to all subsequent visits
- Schedule/confirm the next study visit

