14. CLINICAL OUTCOME ASSESSMENTS

14.1. Investigator Global Assessment (IGA)

The IGA will be performed at all study visits.

If a patient is assessed as “clear” (0) or “almost clear” (1), the patient will not be dispensed the study product. If a patient is assessed as “mild”, “moderate” or “severe” (2, 3 or 4, respectively), study product will be dispensed and the patient will use the study product daily according to patient instructions.

In the event a subject is not dispensed IP at a given visit due to an IGA of "clear" or "almost clear," and the subject's rosacea condition worsens, an unscheduled visit can be performed for assessing the subject and dispensing IP, if appropriate.

The IGA scale provided in [Table 1](#) will be used to describe the severity grade and subsequent score:

Table 1: Investigator Global Assessment (IGA) Scale

Grade	Description
0 – Clear	Skin clear of inflammatory papules or pustules
1 – Almost Clear	Very few small papules or pustules and very mild dull erythema is present
2 – Mild	Few small papules or pustules and mild dull or light pink erythema is present
3 – Moderate	Several to many small or larger papules or pustules and moderate light to bright red erythema is present
4 – Severe	Numerous small and/or larger papules or pustules and severe erythema that is bright red to deep red is present

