15.1. Cutaneous Safety Assessments

A qualified designee will assess local application site cutaneous reactions by rating the dryness and scaling at Baseline, and at all the study visits except the screening visit. The evaluator will determine the score for each of these variables by direct evaluation. The definitions of grades provided in [Table 4](#) will be applied to these evaluations. The Cutaneous Safety Assessment of dryness and scaling will be made by the investigator at the time of the visit.

Table 4: Cutaneous Safety Assessment Scale

Grade	Description
Dryness	
0 – None	No dryness
1 – Mild	Slight but definite dryness
2 – Moderate	Moderate dryness
3 – Severe	Marked dryness and/or cracking
Scaling	
0 – None	No scaling
1 – Mild	Barely perceptible scaling
2 – Moderate	Obvious but not profuse scaling
3 – Severe	Heavy scale production and/or peeling

Application site reactions (dryness and scaling) are not to be recorded as adverse events unless they result in either:

- The temporary discontinuation of the study product.
- The discontinuation of the patient from the study.
- The use of a new concomitant medication in order to treat this event.

Any other application site reaction not listed above (such as pain) should be recorded as adverse events in the source document and eCRFs.

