15.2. Local Tolerability Assessments

A qualified designee will assess local application site tolerability by rating the itching and burning/stinging at Baseline, and at all the study visits except the screening visit. The evaluator will determine the score for each of these variables by asking the patient to grade their experience over the **past 24 hours**. The definitions of grades provided in [Table 5](#) will be applied to these evaluations. The Local Tolerability Assessment evaluations of itching and burning/stinging will be made by the investigator at the time of the visit.

Table 5: Local Tolerability Assessment Scale

Grade	Description
Itching	
0 – None	No itching
1 – Mild	Slight itching, not really bothersome
2 – Moderate	Definite itching that is somewhat bothersome
3 – Severe	Intense itching that may interrupt daily activities and/or sleep
Burning/Stinging	
0 – None	No burning/stinging
1 – Mild	Slight burning/stinging sensation; not really bothersome
2 – Moderate	Definite warm, burning/stinging sensation that is somewhat bothersome
3 – Severe	Hot burning sensation that causes definite discomfort and may interrupt daily activities or sleep

Application site reactions (itching and burning/stinging) are not to be recorded as adverse events unless they result in either:

- The temporary discontinuation of the study product.
- The discontinuation of the patient from the study.
- The use of a new concomitant medication in order to treat this event.

Any other application site reaction not listed above (such as pain) should be recorded as adverse events in the source document and eCRFs.

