8.8.2 Retreatments

The number of retreatments is defined as the number of clinical confirmations of the condition for which the subject was initially treated after the first treatment period with S5G4T-1. For rollover subjects previously treated with vehicle, this is the number of treatments after the initial treatment in 54-07. For rollover subjects previously treated with S5G4T-1, this is the number of treatments in 54-07 following the cessation of the treatment which began in 54-01 or 54-02. A clinical confirmation of the condition will be defined as IGA no longer being clear or almost clear after a previous IGA of clear or almost clear. When a subject has a clear or almost clear IGA in 54-07, it is expected they were instructed not to dose until the IGA reached mild, moderate or severe.

The number of treatment free days until the first retreatment (relapse) will be calculated and summarized. Relapse will be defined as a subject no longer having an IGA of clear or almost clear after a previous visit IGA of clear or almost clear. When a subject has a clear or almost clear IGA in 54-07, it is expected they were instructed not to dose until the IGA reached mild, moderate or severe. Number of treatment free days until first retreatment is defined as the number of days between an initial IGA assessment of clear or almost clear while the subject was receiving S5G4T-1 until an IGA of mild, moderate or severe.

For rollover subjects previously treated with vehicle, the number of treatment free days will be the number of days between the end of their first treatment of S5G4T-1 in 54-07 (when the subject has an IGA of clear or almost clear) and the start of the next treatment in 54-07 (when the

subject has an IGA indicating they should dose) if they treated with S5G4T-1 again or the end of the subject's participation in 54-07. For rollover subjects previously treated with S5G4T-1, the number of treatment free days will be the number of days between the end of the treatment that began in 54-01 or 54-02 (when the subject has an IGA of clear or almost clear) and the start of the next treatment in 54-07 (when the subject has an IGA indicating they should dose) if they treated with S5G4T-1 again or the end of the subject's participation in the 54-07.

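### Assessments at unscheduled visits are discretionary in some protocol passages and required in others, and the SAP can date a restart between visits late or not count it

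*Protocol*

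**What the plan says.** Permissive side: footnote 11 of the rollover flow chart (Protocol 5.2 and 13.9) reads "Perform procedures per PI discretion". Protocol 13.16 opens its list with "The following procedures may be performed at the unscheduled visit, if required". The adverse event query, the IGA, both skin gradings, and weighing and dispensing a pump are separate items in that list, and none is conditional on another.

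Mandatory side: Protocol 14.1 says "The IGA will be performed at all study visits". Protocol 15.1 has a designee "rating the dryness and scaling at Baseline, and at all the study visits except the screening visit", and 15.2 schedules itching and burning/stinging "at Baseline, and at all the study visits except the screening visit". None of the three exempts unscheduled visits. In the flow chart, footnote 8 gives eligibility for product as the purpose of the IGA, and footnote 9 says "The dispensation and usage of the pump is based on IGA score". Section 14.1 adds that if a patient off product worsens, "an unscheduled visit can be performed for assessing the subject and dispensing IP, if appropriate".

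Analysis: SAP 8.8.2 has clinical confirmation of the condition "defined as IGA no longer being clear or almost clear after a previous IGA of clear or almost clear". It ends the treatment-free interval at an IGA of mild or worse, and footnotes a and b of Table 14.2.5 do the same. Protocol 18.3 ends that interval at the start of the next treatment, with no reference to an IGA. SAP 8.1.3 leaves out unscheduled data from before study Day 22, and unscheduled data that map to a visit for which scheduled data exist. It does not say whether 8.8.2 is exempt.

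**The concern.** The unscheduled visit is the protocol's route for restarting product between the 4-weekly visits, and a natural visit for a patient with a skin reaction. It takes place because something has changed, so a score skipped there is not missing at random. If product is restarted with no IGA, or with an IGA that the windowing rule discards, SAP 8.8.2 sees no relapse on that date. The patient is counted as treatment free while applying S5G4T-1. For such patients the error runs one way: time to relapse is too long, or a retreatment is lost. A Kaplan–Meier median with a 95% confidence interval is planned on these times.

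The gradings matter too. The synopsis safety endpoint covers cutaneous and tolerability scores at any time during the trial. Itching and burning/stinging are graded over the past 24 hours, so a grade not taken at an unscheduled visit cannot be recovered later. Reactions of these listed kinds that cause no interruption, withdrawal or new medication stay off the adverse event form.

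**Working it through.** The plan states no figure on this point, so there is none to reproduce. The check compares passages and does day arithmetic.

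Inputs:
- Scheduled 54-07 visits for rollover patients: Days 1, 29, 57, 85, 113, 141, 169, 197, 225, 253 and 281, each post-baseline visit ± 10 days (Protocol 11, SAP 6.1). Nominal spacing is 28 days.
- SAP 8.1.3 windows: they start at Day 22 and run without gaps through Week 40 (Days 267 to 294). The exclusions are those described above.
- SAP 8.8.2: the relapse date is the date of an IGA of 2 or more after an IGA of 0 or 1.

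**1. Would a recorded unscheduled IGA survive the windowing rule?** Take a patient with data at every scheduled visit.
- Days 2 to 280 are 279 days. Removing the 9 nominal visit days (29 to 253) leaves 279 − 9 = 270 possible unscheduled days.
- Days 2 to 21 are 20 days and are not analysed.
- The other 270 − 20 = 250 days map to a visit that already has scheduled data and are excluded.
- Kept: 270 − 20 − 250 = 0.

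Read literally, the rule uses an unscheduled IGA only where a scheduled visit is missing. Making the IGA mandatory would therefore not by itself secure the relapse date.

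**2. How late is the date?** Let product restart u days after a visit scored 0 or 1, with no usable IGA that day and an IGA of 2 or more at the next scheduled visit. Delay = gap − u.
- Nominal gap 28, u from 1 to 27: delay 1 to 27 days, mean 14 if restarts are spread evenly.
- Largest gap within the visit windows: (57 + 10) − (29 − 10) = 67 − 19 = 48 days. Delay is then 1 to 47 days, mean 24.

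**3. Example.** A patient is clear at Day 113 and restarts at an unscheduled visit on Day 120.
- True treatment-free time: 120 − 113 = 7 days.
- Next IGA (Day 141) is 2 or more: 141 − 113 = 28 days recorded.
- Next IGA is 0 or 1: no event is recorded at Day 141.
- An IGA taken on Day 120 falls in the Week 16 window (Days 99 to 126), which already holds the Day 113 visit, so 8.1.3 would exclude it.

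**4. Late or missed?** The documents do not give the chance that the IGA is still 2 or more at the next visit. If it is assumed to lie between 25% and 90%, then 75% to 10% of such restarts would be missed at that visit and the rest dated late.

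**5. Tolerability tables.** Under the same rule, unscheduled grades enter the by-visit summaries only where the scheduled visit has no data. What is lost by not grading is therefore mainly in the by-subject listings.

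**The case against.** The strongest reply is that the protocol does not allow a restart without an IGA. Footnotes 8 and 9 sit in the same chart as footnote 11, the dispensing row is marked for unscheduled visits, and Section 14.1 ties dispensing to an IGA of 2, 3 or 4. A specific rule limits a general note on discretion. This stands. A reader might infer that footnote 11 authorises a restart with no IGA, but the documents do not support that; such a restart would contradict footnote 9 and Section 14.1. What remains is that 13.16, the section a site follows on the day, does not link dispensing to the IGA.

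It is also fair that SAP 8.8.2 uses treatment language: it counts treatments and refers to the start of the next one. But it qualifies that start by an IGA indicating dosing, and it assumes that patients scored 0 or 1 did not dose, without checking the dosing record.

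On safety, adverse event capture does not rest on 13.16. Protocol 16.4 requires all events, observed or reported, to be documented, and each scheduled on-treatment visit asks about events since the previous visit. Reactions leading to interruption, withdrawal or new medication must be recorded as adverse events. A reader might infer that the safety results are tilted in the product's favour; given these provisions and the windowing rule, the documents do not show that.

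Finally, both Protocol 18.3 and SAP 7.1 say that the study is not intended to assess efficacy. That limits the weight of the point but does not remove the inconsistency.

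**Conclusion.** The protocol passages conflict on which assessments are required at an unscheduled visit and must be reconciled. Separately, SAP 8.8.2 and 8.1.3 together leave a restart between visits open to being dated 1 to 27 days late on nominal spacing (up to 47 at the window limits), or not counted if the next IGA is 0 or 1.

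This rests on two conditions. Either no IGA was taken at the restart, contrary to footnote 9 and Section 14.1, or one was taken and 8.1.3 is applied literally to 8.8.2. The documents give no frequency for either.

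A reader might also take the extreme case from the example, 281 − 113 = 168 treatment-free days, as typical. It needs an IGA of 0 or 1 at all six later visits (Days 141 to 281), and it would be a censored time, not an observed relapse time.

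The quantities affected are the descriptive time to relapse and number of retreatments. The main safety summaries are not materially affected. The point is worth correcting because the error runs in one direction and the data needed to remove it are already collected.

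**What to change.** (1) Align Protocol 13.16 and footnote 11 of 5.2 and 13.9 with Sections 14.1, 15.1 and 15.2. State which assessments (IGA, cutaneous safety, local tolerability, adverse event query) are required at an unscheduled visit, at least whenever product is dispensed or a skin reaction prompts the visit. Other procedures can stay discretionary. The matching footnote 9 in the new-patient charts (5.3, 13.10) has no practical effect, because SAP 10 records that no new patients were enrolled. Cost: a few minutes of grading at visits already taking place, and an amendment that needs IRB approval under Protocol 19.2. It helps only visits still to come.

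(2) In SAP 8.8.2, state that relapse and retreatment use all IGAs, including unscheduled ones, and are exempt from the 8.1.3 windowing rule. Add that where dosing or dispensing records show a restart after an IGA of 0 or 1 and no IGA exists on that date, the treatment-free interval ends and a retreatment is counted at the restart date. This also brings the SAP back to the interval in Protocol 18.3. The records are already planned for Listings 16.2.5.3 and 16.2.5.4, and the SAP Preface allows updates before database lock. Cost: a few lines of text and some programming, with no new data.

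No view is taken on the dispensing rule itself.

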5.3. Study Flow Chart for new patients only

Procedure	Visit 1 ¹	Visit 2	Visit 3, 4, 6, 7, 9, 10, 12, 13	Visit 5, 8, 11, 14	Visit 15 (EOT ² /EOS ³)	Unscheduled Visit ⁹
Name of Visit	Screening -35 to 0	Baseline Day 1	Week 4, 8, 16, 20, 28, 32, 40, 44 Day 29, 57, 113, 141, 197, 225, 281, 309	Week 12, 24, 36, 48 Day 85, 169, 253, 336	Week 52 Day 365 ⁴	
Visit window			± 10 days	± 10 days	± 10 days	
Inclusion/Exclusion Criteria	X	X				
Demographics	X					
Medical History/Previous Therapies	X	X				
Sign Informed Consent	X					
Brief Physical Examination		X		X	X	X
Concomitant Therapy and Medication History Reviewed	X	X	X	X	X	X
Pregnancy Test ⁵	X	X	X	X	X	X
Cutaneous Safety Assessment and Local Tolerability Assessments		X	X	X	X	X
Administer/ Review Patient Instructions		X	X	X		X
IGA ⁶	X	X	X	X	X	X
Inflammatory Lesion Count	X	X				
Rosacea Erythema Assessment		X	X	X	X	X
Telangiectasia Assessment		X	X	X	X	X
Weigh Study Product		X	X	X	X	X
Study Product Dispensed ⁷		X	X	X		X
Provide Cleanser and Moisturizer/ Sunscreen, if needed		X	X	X		X
Study Product Collected			X	X	X	
Diary Card dispensed		X	X	X		X
Diary Card collected			X	X	X	X
Adverse Events	X	X	X	X	X	X
Complete RosaQoL ⁸		X		X	X	

¹ Patient will be eligible for the study only after meeting all Inclusion/Exclusion criteria.

² EOT – end of treatment.

³ EOS – end of study.

⁴ All Week 52 procedures should be completed for Patients who terminate early.

⁵ Urine test for women of childbearing potential.

⁶ For product dispensing eligibility

⁷ The dispensation and usage of the pump is based on IGA score.

⁸ RosaQoL is a Rosacea Quality of Life questionnaire

⁹ Perform procedures per PI discretion.

6. LIST OF ABBREVIATIONS AND TERMS

AE(s)	Adverse Event(s)
BPO	Benzoyl Peroxide
°C	Degrees Centigrade
CFR	Code of Federal Regulations
CRO	Contract Research Organization
E-BPO	Encapsulated Benzoyl Peroxide
eCRF	Electronic Case Report Form
EDC	Electronic Data Capture
FDA	Food and Drug Administration
G	Grams
cGCP	current Good Clinical Practice
H	hour(s)
IB	Investigator's Brochure
ICF	Informed Consent Form
ICH	International Conference on Harmonization
IGA	Investigator's Global Assessment
IND	Investigational New Drug
IRB	Institutional Review Board
ITT	Intent-to-Treat
IWRS	Interactive Web Response System
MCMC	Markov Chain Monte Carlo
MedDRA	Medical Dictionary for Regulatory Activities
min	Minutes
mg	Milligram
OTC	Over-the-Counter
PP	Per Protocol
SAE	Serious Adverse Event
SOP	Standard Operating Procedure

7. INTRODUCTION AND BACKGROUND

S5G4T-1 is an innovative topical formulation containing 5% encapsulated benzoyl peroxide (E-BPO) that Sol-Gel is developing for the treatment of rosacea. If approved, S5G4T-1 will be the first product containing E-BPO for the treatment of rosacea. Sol-Gel believes S5G4T-1 has the potential to be as tolerable as, and more effective than, currently marketed rosacea drugs.

[figure not shown]
Rosacea is a chronic and recurrent inflammatory dermatological disorder of unknown etiology. The disease is common, especially in fair-skinned people of Celtic and northern European heritage. The onset of the disorder is usually between the ages of 30 and 50. Early stages of the disease affect women more often than men at a ratio of 3 to 1 (Jansen and Plewig 1997 and McDonnell and Tomecki 2000). Rosacea usually starts as flushing and subtle redness on the cheeks, nose, chin or forehead. Alcohol, hot drinks, spicy foods, stress, sunlight and extreme heat or cold can trigger the onset of this disease. If left untreated, rosacea can slowly worsen over time. As the condition progresses, patients experience inflammatory lesions (papules and pustules), vivid erythema and telangiectasia. Patients may develop furuncles, cystic nodules, granulomas and tissue hypertrophy, sometimes leading to rhinophyma.

The first report on the treatment of rosacea with benzoyl peroxide as a single agent was described by in Montes *et al.* in 1983. In this limited study, 5% benzoyl peroxide, after 5 to 8 weeks of treatment, demonstrated superiority compared to control with respect to papules, pustules and erythema but not telangiectasia. The formulation was a basic formulation with benzoyl peroxide dissolved and delivered in acetone. Irritation and burning was reported in both groups, most likely due to the well-known effects of benzoyl peroxide.

More recently, Breneman *et al.* 2004 published the results of a study in collaboration with J. Leyden. This study was a double-blind, vehicle-controlled study, using a combination gel product of 5% benzoyl peroxide and 1% clindamycin to treat patients having moderate to severe rosacea. The most dramatic effect of the benzoyl peroxide/clindamycin treatment was on the reduction of papules and pustules. Side effects included the well-known effects of benzoyl peroxide, burning and itching.

The most prevalent AEs associated with topical BPO were related to local irritation. These included dry skin, peeling, burning and erythema. For the published studies, the percentage of subjects with dermatological adverse events considered possibly related to BPO monotherapy ranged from 7% (Thiboutot *et al.* 2007) to 22% (Tschen *et al.* 2001). In studies sponsored by Sol-Gel, the percentage of subjects with dermatological adverse events associated with E-BPO, 7% ranged from 0% (Study SGT-03B) to 37% (Study SGT-04), and the incidence associated with lower concentrations of E-BPO was 2% or less.

Several published studies reported AEs that might be associated with sensitivity of subjects to BPO. [Leyden *et al.* 2001](#) reported that 1 of 164 subjects (0.6%) receiving 5% BPO had an allergic reaction, and that allergic reactions occurred for 1.2% of subjects receiving 5% BPO plus 1% clindamycin and for 3.1% of subjects receiving 5% BPO plus 3% erythromycin. [Tschen *et al.* 2001](#) reported a rash for 1 of 95 subjects (1%) that received 5% BPO monotherapy. [Fyrand and Jakobsen 1986](#) reported that 2 of 49 subjects withdrew from the study due to severe dermatitis indicating possible sensitization. [Montes *et al.* 1983](#) reported hypersensitivity to BPO in 4 of 31 subjects receiving 5% BPO acetone gel for rosacea. [Weiss *et al.* 2002](#) reported that 2 of 257 subjects receiving BPO plus clindamycin developed urticaria. In Study KGL 5782, 1 subject developed possible delayed contact hypersensitivity to both E-BPO, 2.5%, and Proactiv, 2.5%, indicating the hypersensitivity was probably due to BPO not an excipient. None of these events that might possibly indicate sensitization were confirmed by patch testing.

